#### ANALYSIS:

Measures of the level of glycemic control will be assessed primarily by HbA1c and secondarily by the average glucose tests results on the patient's glucose meter. Comparison of the glucose results (average, range, standard deviation, number of daily tests) between the study entry, 1 week, 1 month and 3 month follow up visits will be done. Comparison of HbA1c at entry and at 3-month follow-up will be performed. Questionnaire scores will be compared between study entry, 1 week follow up, 1 month follow up and 3-month follow-up visits for DES and Stages of Change scales. We will determine if there is a correlation between the scores on the questionnaires and measures of glucose control. We will classify study and control participants into adherent and non-adherent groups.

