#### CONFIDENTIAL

This material is the property of the NYU School of Medicine and Langone Medical Center. Do not disclose or use except as authorized in writing by the study sponsor

Use of continuous glucose monitoring system with intensive feedback in adolescents with poorly controlled type 1 diabetes  
Version Date: 04/26/2018

Dichotomizing participants into adherent and non-adherent:

Study subjects will receive points for calibrating the CGM device and for successfully completing phone contact with the pediatric diabetes team. The patient will receive 2 points for calibrating the device 2 times/day for at least 5 days, 1 point for calibrating the device 2 times on at least 3 days and 0 points for calibrating any less. Similarly the patient will receive 2 points for completing successful phone contact with study personnel for at least 5 days, 1 point for completing phone contact on at least 3 days and 0 point for contact any less than mentioned before. The two scores will be added to get a total score. Patients with scores 3-4 will be classified as adherent and scores 0-2 will be classified as non-adherent. Control subjects who complete 4 or more phone calls on different days will be classified as adherent and those who complete fewer phone calls will be classified as non-adherent.

Statistical methods:

Demographic data will be tabulated. Statistical analysis of questionnaires will be done according to published standards. The paired t-test will be used for comparisons involving stages of change score.

Independent variables will include the empowerment score, average glucoses, HbA1c and whether the subjects fall into the adherent vs. non-adherent groups. Dependent variables include glucose level(s) and stage of change. We will analyze the 7 day average glucose by meter download and categorize the results in terms of change: No change (-15 to + 15), Higher ( $\geq + 15$ ) or Lower ( $\leq -15$ ). We will analyze the HbA1c and categorize the results in terms of change: No change ( $> -0.5$  to  $+ 0.5$ ), Higher ( $\geq + 0.5$ ) or Lower ( $\leq -0.5$ ). Stages of change (Appendix A) will be categorized as unchanged, improved or worsened. In addition, descriptive statistics including quality of life, diabetes knowledge scale, and demographic variables will be tabulated.

Statistical Analysis for sensor study:

Questionnaires:

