Demographics (Appendix G): data will be put in table form, with range, mean, s.d. scores for age; % Male/Female; and descriptive data for the remainder of the items. In Questions #11, 13 and 14, with 1-5 scales, the range, mean, and s.d. scores will be given. Stages of Change (Appendix A): scores can be given categorically, with each question assigned a score of 1 for a “yes” answer, and zero for a “no” answer; then range, mean, s.d. will be calculated before and after the intervention. In addition, a “yes” or “no” answer to these questions will determine which “stage of change” category the subject belongs in, according to the definition of “stages of change”. This is categorical data. We will analyze movement in the “stages of change” by comparing the score before and after the study intervention. This will be categorical: improvement, no change, deterioration.

CONFIDENTIAL

This material is the property of the NYU School of Medicine and Langone Medical Center. Do not disclose or use except as authorized in writing by the study sponsor

Use of continuous glucose monitoring system with intensive feedback in adolescents with poorly controlled type 1 diabetes  
Version Date: 04/26/2018

Diabetes Empowerment Scale-Short Form (Appendix B): the average of the scores of the completed items will be tabulated. Each question is answered as 1-5, and there are 8 questions. Thus, the scores can range from 1-5. The scores will be compared before and after study intervention.

Diabetes Knowledge Test (Appendix C): There are 23 multiple choice questions, scored as correct or incorrect. This will be administered only at baseline.

Peds Quality of Life 3.2 Diabetes Module: (Appendix D): There are 33 questions with Likert scale answers (0-4). Scores are transformed on a scale of 0-100. This test will be administered before and after the study intervention.

PHQ-2: (Appendix E): The score ranges from 0-6. The scores will be compared before and after the study intervention.

CGM Satisfaction Scale: (Appendix F): We are using an abbreviated version of a previously published CGM-SAT scale. Each question is scored 1-5 and the mean is calculated. This will be given after the intervention and only in the intervention group.

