Daily Phone Log: (Appendix H): Scoring will be done for each day of the initial week of the study, in both CGM intervention group, and control group based on the following: Study subjects will receive points for calibrating the CGM device and for successfully completing phone contact with the pediatric diabetes team. The patient will receive 2 points for calibrating the device 2 times/day for at least 5 days, 1 point for calibrating the device 2 times on at least 3 days and 0 points for calibrating any less. Similarly the patient will receive 2 points for completing successful phone contact with study personnel for at least 5 days, 1 point for completing phone contact on at least 3 days and 0 point for contact any less than mentioned before. The two scores will be added to get a total score. Patients with scores 3-4 will be classified as adherent and scores 0-2 will be classified as non-adherent. Control subjects who complete 4 or more phone calls on different days will be classified as adherent and those who complete fewer phone calls will be classified as non-adherent.

The distribution of the data will be assessed using the Kolmogorov-Smirnov test. All categorical variables will be presented as mean +standard deviation. For categorical variables the differences between the compliant and non-compliant groups will be assessed using the Mann Whitney or rank order Wilcoxon test based on normality. For categorical variables independent sample t test will be used. Univariate analysis will be used to establish correlation between variables of interest.

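### The trial randomises 40 to CGMS and 20 to control, but the analysis plan specifies no comparison of the two arms on any outcome

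*Combined protocol and SAP*

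**What the plan says.** The Study Summary describes a randomised open-label design, and SUBJECTS gives 40 to CGMS and 20 to control. AIM asks whether short-term CGMS with intensive feedback changes motivation or behaviour, and its hypothesis mentions feedback or the lack of it.

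The ANALYSIS section then names these contrasts:

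- **Between visits.** Glycaemic control is "assessed primarily by HbA1c and secondarily by the average glucose tests results", and "Comparison of HbA1c at entry and at 3-month follow-up will be performed". Meter glucose, the Diabetes Empowerment Scale (DES) and Stages of Change are compared across entry, 1 week, 1 month and 3 months. Under Statistical methods, "The paired t-test will be used for comparisons involving stages of change score". Movement between stages is judged by "comparing the score before and after the study intervention"; DES and PHQ-2 are treated in the same way.
- **Associations.** Questionnaire scores are correlated with glucose control, and an unspecified univariate analysis is mentioned.
- **Adherence groups.** The independent variables are listed as "Independent variables will include the empowerment score, average glucoses, HbA1c and whether the subjects fall into the adherent vs. non-adherent groups". After the Daily Phone Log paragraph, "differences between the compliant and non-compliant groups will be assessed using the Mann Whitney or rank order Wilcoxon test", followed by "For categorical variables independent sample t test will be used", which names no groups.

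In the analysis text, controls appear only where adherence is classified and the phone log is scored.

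**The concern.** AIM poses a causal question, and the control group is there to answer it. The only contrast that randomisation protects is CGMS versus control, and the plan does not write it down. An analyst following the text would answer the aim with a before-after shift or an adherent/non-adherent difference. Either can appear when the intervention does nothing.

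If an arm comparison is added later, its outcome, visit, test and analysis set would be chosen with open-label data already in hand.

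**Working it through.** **1. What is compared with what.** The documents give no alpha, power, effect size or SD, so there is no sample-size figure to reproduce beyond 40 + 20 = 60. The central check is textual.

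| Outcome | Contrast written in ANALYSIS | CGMS vs control? |
|---|---|---|
| HbA1c | entry vs 3 months; change categories cut at ±0.5 | no |
| Meter glucose | between four visits; change categories cut at ±15 | no |
| Stages of Change | between visits, paired t-test; improved / unchanged / worsened | no |
| DES, PHQ-2 | before vs after (DES also between visits) | no |
| PedsQL | given before and after; tabulated descriptively | no |
| Unnamed variables | compliant vs non-compliant; t test with no groups named | no |

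**2. What a before-after test shows when the intervention has no effect.** Assume both arms shift by the same d, in SDs of change. Power of a two-sided 5% paired t-test comes from the noncentral t with n − 1 degrees of freedom and noncentrality d√n. For n = 60:

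| d | 0.1 | 0.2 | 0.3 | 0.4 | 0.5 |
|---|---|---|---|---|---|
| P(significant) | 12% | 33% | 63% | 86% | 97% |

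The plan names the paired t-test only for the stages-of-change score and does not say whether arms are pooled. If paired tests were run within each arm instead (also not stated), significance in CGMS alone has probability power(40) × (1 − power(20)). At d = 0.3 this is 0.457 × (1 − 0.247) = 34%; at 0.4, 0.694 × (1 − 0.397) = 42%; at 0.5, 0.869 × (1 − 0.565) = 38%.

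**3. Regression to the mean in HbA1c.** Entry requires HbA1c ≥ 8%. Assume a normal population with mean 8.0–9.0, SD 1.2–1.8 and correlation r = 0.7–0.9 between measurements. If the qualifying value is also the entry value, the expected fall is (1 − r) × (E[X | X ≥ 8] − mean).

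- Largest: mean 8.0, SD 1.8, r = 0.7. The excess is 1.8 × 0.798 = 1.436, and 0.3 × 1.436 = 0.43 points.
- Smallest: mean 9.0, SD 1.2, r = 0.9. The excess is 0.424, and 0.1 × 0.424 = 0.04 points.

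The screening section takes the qualifying HbA1c from the medical record, while METHODS has HbA1c measured in the lab at entry. If these are separate values, the fall is 0 when the record value correlates equally with both later values, and (r − r²) × excess = 0.04–0.30 points if the correlation decays from r to r².

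**4. Whether adherence can stand in for arm.** A CGMS participant scores 0–2 for calibration and 0–2 for calls (2 points for at least 5 days, 1 point for 3–4 days) and needs a total of 3. For controls, "Control subjects who complete 4 or more phone calls on different days will be classified as adherent". Assume 7 days, daily probability p for each task, and independence. Then P(control adherent) = P(Bin(7, p) ≥ 4). For CGMS it is A² + 2AB, with A = P(≥ 5 days) and B = P(3 or 4 days). At p = 0.5, A = 0.227 and B = 0.547, giving 0.052 + 0.248 = 0.30.

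| p | 0.5 | 0.6 | 0.7 | 0.8 |
|---|---|---|---|---|
| Control adherent | 50% | 71% | 87% | 97% |
| CGMS adherent | 30% | 58% | 84% | 97% |

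The same underlying behaviour can therefore earn a different label depending on arm. If calls and calibration always fell on the same days, CGMS adherence would equal A: 23% / 42% / 65% / 85%.

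**5. Precision of the missing comparison.** SE = SD × √(1/40 + 1/20) = 0.274 × SD. With t(58) = 2.00, the 95% half-width for change in HbA1c is 0.44 points at an assumed SD of 0.8 and 0.82 at 1.5. With 20% missing in each arm (32 vs 16), SE = 0.306 × SD and t(46) = 2.01, giving 0.49–0.92. For the proportion improving in stage of change, 1.96 × 0.274 × √(p(1 − p)) is 25 percentage points at p = 0.3 and 27 at p = 0.5, with all 60 observed.

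**The case against.** The best defence is that an arm comparison is plainly intended. The design is randomised, the hypothesis mentions feedback or its absence, both arms attend the same visits, the list of independent variables is open-ended, and the t test with unnamed groups could be the comparison of arms. All of that is fair: the plan does not exclude an arm comparison. But it attaches no outcome, visit, test or analysis set to one, and the unnamed t test directly follows the compliant/non-compliant sentence. An intention left unwritten is not a pre-specified analysis.

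The listed empowerment score does serve the part of the hypothesis about self-efficacy, so the list is not wrong in itself. It is incomplete for the part about the intervention.

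The illustrations have limits. The pooled false-signal rate is only 12% for a 0.1 SD shift. Paired tests by arm are not in the plan. Regression to the mean may be nil. The gap in adherence labels closes at 80% daily completion under independence. These points limit the size of the problem in particular circumstances; they do not supply the missing comparison.

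**Conclusion.** The concern holds and should be fixed before analysis. No CGMS-versus-control comparison is specified on any outcome, and the analyses that are specified cannot separate the assigned intervention from time, participation effects, regression to the mean or differences in who adheres. This rests on the text alone.

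The sizes rest on assumed values that the documents do not give. With a common shift of 0.1 to 0.5 SD and no intervention effect, a pooled paired test is significant in 12% to 97% of trials. Regression to the mean in HbA1c ranges from 0 to 0.43 points, depending on whether the qualifying value is reused as the entry value and on the assumed distribution and correlation. The difference in adherence rules between arms is a fact of the plan; only its numerical effect depends on assumptions.

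**What to change.** Add randomised arm to the independent variables, and make CGMS versus control, with all participants in the arm assigned, the main analysis of each key outcome. The sponsor should choose which outcome leads in light of AIM, and name the visit for each.

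- **HbA1c at 3 months:** ANCOVA on arm and entry HbA1c, reporting the difference with its 95% CI.
- **Stage of change at the named visit:** improved / unchanged / worsened compared between arms, for example by a rank-sum test, with the difference in proportion improving and its 95% CI.
- **DES, PedsQL, PHQ-2 and meter average:** the same baseline-adjusted arm comparison, as supporting analyses.
- **Missing 3-month values:** state how they are handled and report them by arm.
- **Interpretation:** state what contact controls receive. METHODS and CONSENT tie the daily calls to wearing the device, while the phone log is scored in both arms. The contrast estimates the effect of the assigned package, not of CGM alone.
- **Paired and adherence analyses:** keep them as descriptive, and do not infer an effect from significance in one arm and not the other.

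No new data are needed, since arm and entry values are already collected. The cost is a few paragraphs of text and a less precise result than a before-after analysis would suggest. The half-widths above are for unadjusted change; adjustment for entry HbA1c may narrow them and missing data will widen them. That imprecision comes from 40 versus 20, and a before-after result would hide it.

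### Average glucose and HbA1c are listed as predictors of glucose level with no time points, and randomised arm is not among the predictors

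*Combined protocol and SAP*

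**What the plan says.** Under Statistical methods, the combined protocol and SAP gives two lists. The first reads "Independent variables will include the empowerment score, average glucoses, HbA1c and whether the subjects fall into the adherent vs. non-adherent groups". The second reads "Dependent variables include glucose level(s) and stage of change". Neither gives a visit, and neither says which predictors serve which outcome.

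The same paragraph then treats both glycaemic measures as results: "We will analyze the 7 day average glucose by meter download and categorize the results in terms of change" and "We will analyze the HbA1c and categorize the results in terms of change". The ANALYSIS section ranks them: "Measures of the level of glycemic control will be assessed primarily by HbA1c and secondarily by the average glucose tests results". It also plans a before-and-after look at the first-ranked measure: "Comparison of HbA1c at entry and at 3-month follow-up will be performed".

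The only method named for relating variables to one another comes at the end of the statistical text, after the Daily Phone Log: "Univariate analysis will be used to establish correlation between variables of interest".

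**The concern.** The introduction defines HbA1c as reflecting mean blood glucose across the preceding 60 to 90 days. HbA1c and a meter average from the same visit are thus two readings of nearly the same thing. If one is used to explain the other, a strong association is expected whether or not the device does anything.

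Two omissions add to this. Randomised arm is not an independent variable, so the list never connects an outcome to CGMS or control. HbA1c is first in rank under ANALYSIS but appears in these lists only as a predictor.

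At stake is the trial's main glycaemic question. Followed literally, the list yields associations within glycaemia and no arm comparison. If it is repaired by adding arm alone, with the time points still open, the analyst could condition on a value that the intervention is meant to change. Leaving several readings open in a trial of 60 also allows the model to be chosen after the results are seen.

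**Working it through.** **Which values could be meant.** The study phases and ANALYSIS give these collection times:

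| Variable | Entry | 1 week | 1 month | 3 months |
|---|---|---|---|---|
| Meter average | yes | yes | yes | yes |
| HbA1c | yes | no | no | yes |
| Stage of change | yes | yes | yes | yes |

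Both glycaemic measures therefore have an entry value and at least one post-randomisation value. The list cannot be assumed to mean entry values throughout, because the adherence grouping in it is built from first-week calibration and phone calls, after randomisation. Elsewhere the plan does limit a measure to baseline (the Diabetes Knowledge Test); here it does not.

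**What the choice of time point does once arm is in a model.** The plan states no effect size, SD or alpha, so there is no figure of its own to reproduce. The calculation below shows only the consequence of each reading.

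Take a linear model of follow-up glucose on arm and one covariate. The arm coefficient is

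arm coefficient = d_g − b × d_c

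where d_g is the device effect on glucose, d_c is the arm difference in the covariate, and b is the within-arm slope of glucose on the covariate.

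- *Entry value as covariate.* Randomisation makes d_c = 0 in expectation, so the coefficient is d_g and nothing is lost.
- *Follow-up HbA1c as covariate.* Assume both measures are in SD units, both shift by d, and their within-arm correlation is ρ. Then b = ρ and the coefficient is d − ρd = d(1 − ρ).

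Assumptions, none from the documents: d = −0.5 SD on both measures; a latent correlation of 0.6 between entry and follow-up glycaemia; ρ from 0.5 to 1.0. The allocation is the plan's 40:20, that is 2:1. A large-sample simulation (600,000 subjects) gave:

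| ρ | Unadjusted | Adjusted for entry value | Adjusted for follow-up HbA1c | Formula d(1 − ρ) | Share removed |
|---|---|---|---|---|---|
| 0.5 | −0.502 | −0.500 | −0.252 | −0.5 × 0.5 = −0.25 | 50% |
| 0.7 | −0.500 | −0.499 | −0.148 | −0.5 × 0.3 = −0.15 | 70% |
| 0.9 | −0.497 | −0.500 | −0.051 | −0.5 × 0.1 = −0.05 | 90% |
| 1.0 | −0.498 | −0.499 | 0.000 | −0.5 × 0 = 0 | 100% |

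The last row is the case of the same variable on both sides.

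**What holds without any joint model.** The near-tautology needs no arm term and no regression. A univariate correlation of 3-month HbA1c with the 3-month meter average already has it.

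**The case against.** A reader might infer that the plan will regress glycaemia on itself and so cancel the device effect. The documents do not support that, for four reasons.

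1. No multivariable model is named. The stated method is univariate, and in a univariate analysis one predictor cannot adjust away another.
2. Arm is not in the list, so the list contains no device estimate to remove. The model with arm beside follow-up HbA1c is hypothetical.
3. No time point is given. If entry values are meant, this is ordinary baseline adjustment and harmless. HbA1c is measured only at entry and 3 months, so a same-visit HbA1c analysis after entry can arise only at 3 months. Glycaemia is also a legitimate predictor of the other dependent variable, stage of change.
4. HbA1c is not merely a predictor in the plan. Its change is categorised as a result in the same paragraph, and entry is compared with 3 months under ANALYSIS. The dependent list is also worded as non-exhaustive.

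Nor should complete loss of the effect be presented as expected. It arises when ρ = 1, or when the device is assumed to act on meter glucose only through HbA1c. For example, with an assumed −0.8 HbA1c points and an assumed 28 mg/dl per point, d_g = 28 × (−0.8) = −22.4 mg/dl, and the adjusted coefficient is −22.4 − 28 × (−0.8) = 0. That zero is built into the assumptions.

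All four points stand, and they limit the claim. They do not remove the undefined time points and roles, the missing arm, or the emptiness of a same-visit association between two glycaemic measures. A ban on every use of follow-up glycaemia as a predictor would also go too far, because ANALYSIS plans to correlate questionnaire scores with glucose control, which is a fair exploratory question.

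**Conclusion.** The point holds as a defect of specification. The lists put glycaemia on both sides without time points, omit randomised arm, and leave the first-ranked glycaemic measure off the dependent list although it is treated as a result elsewhere. Followed as written, they relate glycaemia to itself and never to CGMS versus control. More broadly, the analysis sections name no test of CGMS against control on glucose or HbA1c.

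The size is conditional. Should arm be added beside follow-up glycaemia, 50% to 100% of a device effect on glucose would be removed for assumed correlations of 0.5 to 1.0, with an equal standardised effect assumed on both measures. Adjustment for entry values removes none. The direction is secure wherever the device lowers both measures and they are positively correlated within arm; the percentages are illustrations. The change should be made before analysis.

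**What to change.** Replace the two lists with a stated model for the intervention effect:

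- **Outcomes, in order:** 3-month HbA1c; average meter glucose at a named follow-up visit; stage of change at a named follow-up visit, with a model suited to its scale.
- **Predictors:** randomised arm and the entry value of that outcome, with entry empowerment score as an option.
- **Excluded from these models:** any post-randomisation glucose, HbA1c or adherence variable. Adherence is observed after randomisation and is scored differently in the two arms.

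Keep the correlations between questionnaires and glycaemia, and the comparisons of adherent with non-adherent participants, as separate analyses. Label them exploratory and state the visit for each variable.

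The cost is analysis wording only, since every value needed is already collected.

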## Use of continuous glucose monitoring system with intensive feedback in adolescents with poorly controlled type 1 diabetes

Version Date: 04/26/2018

Type 1 diabetes (T1D) is one of the most common chronic diseases presenting in childhood. The prevalence ranges from 1 case per 1430 children at 5 years of age to 1 case in 360 at 16 years of age worldwide in the last few years. The incidence of T1DM has increased by about 2-3 % each year. Management of T1D requires frequent blood glucose monitoring, insulin injections and careful attention to diet. Hemoglobin A1c is a measure of average blood glucose over the prior 60-90 days. The 2014 ADA goal for target HbA1c in adolescents is below 7.5 % but this is seldom achieved. There are multiple challenges to managing T1D in adolescents. The insulin requirements are constantly changing as adolescents go through puberty, lead more independent lives and make their own food choices. In addition, adolescents may not feel the need to work hard to control their diabetes as they feel healthy and have a sense of invulnerability and immortality. Tight blood glucose control requires frequent changes in the insulin regimen and pattern recognition. Even when patients check blood glucose levels regularly, it is measured only 4-8 times per day while fluctuations in blood glucose occur continuously. Introduction of continuous glucose monitoring (CGM) provides a measure of blood glucose level every 5 minutes. CGM is FDA approved for use in children as an adjunct to but not a replacement for capillary blood glucose testing. In the Type 1D exchange clinic registry {Wong, 2014 #75}, 9 % of over 17,000 participants used CGM (6% of children <13 years old, 4% of adolescents 13 to <18 years, 6% of young adults 18 to <26 years, and 21% of adults ≥26 years). On July 21, an FDA advisory panel voted 8-2 to allow patients to use Dexcom's G5 CGM data for making treatment decisions without a finger stick verification. Society representative [name] testified in support of the label change citing the device's safety and the need for additional guidance on how to use unverified CGM data effectively. The panel's recommendation will now be considered by the FDA which, if accepted, will carve a path forward for Medicare coverage of the device. Currently CGM is not universally covered by private insurance. This wealth of information could theoretically allow adolescents to understand their diabetes better as well as help the physician in making changes in insulin regimen while avoiding hypoglycemia. Studies in adults have shown CGM significantly lowers HbA1c levels without increasing risk for hypoglycemia. However research has shown that HbA1c did not improve in adolescents with T1D placed on CGM (presumably due to the lack of consistent use) but HbA1c was lowered in young children and adults on CGM. While development of a closed loop system for diabetes management will require CGM, adolescents are often resistant to wearing the CGM device.

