#### CONFIDENTIAL

This material is the property of the NYU School of Medicine and Langone Medical Center. Do not disclose or use except as authorized in writing by the study sponsor

Use of continuous glucose monitoring system with intensive feedback in adolescents with poorly controlled type 1 diabetes  
Version Date: 04/26/2018

appointments and staff will determine if they are interested in participation in the study using a recruitment script uploaded under recruitment materials section.

The study is minimal risk (MR). The device is approved by the FDA and is being used according to its cleared/approved labeling. The probability and magnitude of harm or discomfort anticipated in this research is similar to those ordinarily encountered in daily life or during the performance of routine physical or psychological examinations or tests.

The use of the CGMS will be described.

The study will consist of 4 phases.

1: For all participants at entry into the study the participant's HbA1c will be measured in the lab at the location of the patient's visit and his/her glucose meter will be downloaded as part of routine care. The average capillary glucose level, (with range and standard deviation) and the average number of tests per day over the prior 14 days will be recorded. The current individual care plans for self-management of type 1 diabetes will be reviewed by the study personnel with the participant.

Questionnaires will be administered to all the participants except Appendix F:

- 1) Appendix A - Stages of Change measure (original). We created a 5 item questionnaire to assess the patient's current stage.
- 2) Appendix B - Psychosocial self-efficacy (University of Michigan Diabetes Research and Training Diabetes Empowerment Scale short-form) - DES. 8 items. Also available for use.(3-6)
- 3) Appendix C - Knowledge and risk perception (University of Michigan Diabetes Research Training Center Diabetes Knowledge Scale). 23 items - DKT. We are substituting rapid acting insulin for NPH insulin in item 17 since NPH is not used in our study population. Available for use without permission as long as the source is quoted.(7, 8)
- 4) Appendix D - Quality of life (Peds QL 3.2, Diabetes module,) – Peds QL. 33 items on a Likert scale.(9)

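### The glucose and HbA1c change categories share limits (+15, -15 and HbA1c +0.5), and the +/-15 glucose band has no unit or rationale and may be narrow for a 7-day meter average

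*Combined protocol and SAP*

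**What the plan says.** The ANALYSIS section assesses glycemic control primarily by HbA1c and secondarily by the meter average. It plans comparisons of the glucose results, including the number of daily tests, across visits, and of HbA1c between entry and 3 months.

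Statistical methods then adds a three-way rule. For glucose it uses the "7 day average glucose by meter download and categorize the results in terms of change: No change (-15 to + 15"; *Higher* starts at +15 inclusive and *Lower* at -15 inclusive. For HbA1c the text reads "We will analyze the HbA1c and categorize the results in terms of change: No change", running from above -0.5 up to +0.5, with *Higher* from +0.5 inclusive and *Lower* from -0.5 inclusive. No unit, source or reliability figure accompanies the 15.

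Two other places bear on the rule. In METHODS, phase 1, the meter download covers a different period: "the average number of tests per day over the prior 14 days will be recorded", in the same sentence as the average glucose, and later visits extract the data in the same way. The background says that even in patients who test regularly, "it is measured only 4-8 times per day while fluctuations in blood glucose occur continuously".

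**The concern.** A classification rule should give every possible value one label. This one does not, and one of the ambiguous values lies on HbA1c, the leading glycemic measure. With 20 controls, relabelling one control patient moves that arm's percentage by 1/20 = 5 points; in the 40-patient CGMS arm it moves by 1/40 = 2.5 points.

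The second question is whether 15 is wide enough. A 7-day average of spot readings carries sampling error, and the difference of two such averages carries more. If that error is comparable with 15, part of the *Higher* and *Lower* counts is ordinary fluctuation, and participants who test least are mislabelled most. Testing frequency may also differ by group. During the device week, CGMS participants are told to calibrate at least twice daily and to confirm extreme sensor readings by meter, and no such instruction is stated for controls. Calibration also enters the adherence score, which is then used as an independent variable.

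**Working it through.** The plan gives no SD, misclassification rate or basis for the 15, so there is no figure of its own to reproduce.

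**Shared limits, read from the text**

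| Change | Labels that apply |
|---|---|
| Glucose +15 | No change, Higher |
| Glucose -15 | No change, Lower |
| HbA1c +0.5 | No change, Higher |
| HbA1c -0.5 | Lower only |

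**How often a value falls on a shared limit.** Assume a normal change centred on zero, glucose rounded to 1 mg/dl and HbA1c to 0.1.
- Glucose: P = 2 x [Phi(15.5/s) - Phi(14.5/s)]. For an assumed SD of change s of 10, 15, 20 and 30 this is 2.6%, 3.2%, 3.0% and 2.4%.
- HbA1c: P = Phi(0.55/s) - Phi(0.45/s). For an assumed s of 0.2, 0.3, 0.5, 0.8 and 1.0 this is 0.9%, 3.3%, 4.8%, 4.1% and 3.5%, or 0.6, 2.0, 2.9, 2.5 and 2.1 of 60 patients.

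**Width of the +/-15 band**

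Inputs:
- Tests per day: 4 to 8 (background text), so n = 7 x 4 = 28 to 7 x 8 = 56 readings a week. The background figure describes regular testers; 2 a day is added as an assumption.
- SD of single readings: not given. METHODS only lists it as something to record. Assumed 40 to 100 mg/dl.
- Unit: assumed mg/dl, from the sensor alarm limits in METHODS.
- Readings independent; no true change.

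Formulas: SD of the difference of two 7-day means, s = SD x sqrt(2/n). P(labelled changed) = 2 x [1 - Phi(15/s)].

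Example, SD 80 and 4 tests a day: s = 80 x sqrt(2/28) = 21.4; 15/21.4 = 0.70; P = 48%.

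| Assumed SD (mg/dl) | 8/day | 6/day | 4/day | 2/day |
|---|---|---|---|---|
| 40 | 5% | 9% | 16% | 32% |
| 60 | 19% | 25% | 35% | 51% |
| 80 | 32% | 39% | 48% | 62% |
| 100 | 43% | 49% | 57% | 69% |

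Across 4 to 8 tests a day, s runs from 7.6 (SD 40, 8/day) to 26.7 (SD 100, 4/day). The band is thus about 2 SDs of the change at one end (15/7.6) and 0.6 at the other (15/26.7).

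**Break-even.** For at most 5% of stable patients to be mislabelled, s must not exceed 15/1.96 = 7.65, so the SD of a weekly mean must not exceed 7.65/sqrt(2) = 5.4 mg/dl. In single readings that is 5.41 x sqrt(56) = 40 at 8 tests a day, or 5.41 x sqrt(28) = 29 at 4.

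**Effect of the window.** With 14 days at both time points, the example has n = 56, s = 15.1 and P = 32% instead of 48%. A 14-day window at the 1-week visit would, however, include 14 - 7 = 7 days from before study entry.

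**The case against.** The strongest reply is that the width argument rests wholly on assumed variability. That stands: no section gives a within-patient or week-to-week SD, and at SD 40 with 8 tests a day only about 5% are mislabelled. The independence assumption can also err either way. Positive correlation between readings would raise the rates. A regular time-of-day pattern, sampled alike in both weeks, would inflate the spot SD without adding to the difference, and so lower them. A reader might infer that the band is narrower than normal weekly fluctuation; the documents do not establish that.

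A reader might also infer that the shared limits themselves cause many stable patients to be called changed. They do not: only values exactly on a limit are affected.

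Nor do the documents support reading the HbA1c asymmetry as flattering the result. A rise of 0.5 is ambiguous, since the text also puts it in *Higher*, and the same rule applies to both arms. Random mislabelling mainly adds noise to both arms unless testing frequency differs between them.

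Finally, meter glucose is secondary, and ANALYSIS already compares the underlying glucose values, number of tests and HbA1c between visits. That limits the harm but does not remove it, because no by-arm estimate or confidence interval is named for either measure. The paired t-test is assigned to the stages of change score, and the remaining tests compare compliant with non-compliant groups.

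It could also be said that an analyst would let the explicit inequality signs decide the ties. Probably so, but two analysts could differ, and the choice should not be left until the data are seen.

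**Conclusion.** The overlaps at glucose +15 and -15 and at HbA1c +0.5 are certain from the text, as are the missing unit and rationale. Their direct effect is small: about 2-3% of patients for glucose and 1-5% for HbA1c, given the assumed rounding and SDs of change.

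Whether the +/-15 band is too narrow is conditional. At the documents' 4 to 8 tests a day, the share of stable patients labelled as changed runs from about 5% to 57% over an assumed SD of 40 to 100 mg/dl. It is 19% or more once the SD reaches 60, and higher with fewer tests. The plan offers nothing to place the trial within that range, so the width needs justification before the counts are interpreted. The 7-day and 14-day windows are a separate inconsistency on the same measure. The point merits correction but does not undermine the trial.

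**What to change.** In Statistical methods:
- Make the bands exclusive and symmetric, with the unit: *No change* above -15 and below +15 mg/dl, and above -0.5 and below +0.5 for HbA1c; *Higher* at +15 or +0.5 and above; *Lower* at -15 or -0.5 and below. Give the reason for 15.
- Base the glycemic conclusions on continuous change in HbA1c and in average glucose: mean change by arm and the between-arm difference, each with a 95% confidence interval. Keep the categories as description.
- Report the number of meter readings behind each average, by arm and visit.
- Reconcile the 7-day window here with the 14-day window in METHODS, phase 1, taking account of what each covers at the 1-week visit.

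The same downloads and laboratory values are used, so the cost is wording. The downside is that the three-way classification becomes descriptive only.
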